2.3.4 Pharmacodynamic profiles

As a prodrug, parecoxib undergoes a full and swift bioconversion to valdecoxib which is its pharmacologically-active metabolite. The dose of valdecoxib needed to block the activity of COX-2 by half is 0.005μ mol / L and this is much greater higher than the half maximal inhibitory dose for COX-1 activity which is 140 μ mol/L (Talley *et al.*, 2000).

With respect to its analgesic effect, paracoxib's efficacy has been demonstrated in patients with postoperative pain following third molar extraction, gynaecological and orthorthopaedic surgery (Barden *et al.*, 2003; Martinez *et al.*, 2007; Mohamad *et al.*, 2014). The analgesic activity of IV parecoxib can also be conspicuously observed in a

murine model of acute inflammation and pain brought about by carrageenan (Talley *et al.*, 2000). Talley and co-workers (2000) demonstrated that the IV parecoxib dosed at 30 mg/kg produced a quick onset of action, resulting in a total reduction of nociceptive sensitivity (hyperalgesia) within 1 hour following its administration (Talley *et al.*, 2000). The authors also established that a parecoxib dose of 5mg/kg was required to create analgesic effects in half of the rats in their murine model. Besides, they also showed that a parecoxib dose of 30 mg/kg produce equivalent clinical end-points as ketorolac administered in the same dose (Talley *et al.*, 2000).

With regard to its gastrointestinal side effects, Hubbard et al. (2000) established, in a double-blind RCT, that normal elderly individuals (aged between 65 and 75 years old) who were administered with 40 mg IV parecoxib twice daily for 7 days (n=31) had significantly less susceptibility to gastrointestinal ulceration than those who received 15 mg IV ketorolac group 4 times a day for 5 days after which they were given placebo for 2 days (n=31) (0 vs 23%, p<0.05). Moreover, the number of new cases of gastrointestinal lesions (both erosions and ulcers) was also significantly less in parecoxib group. Based upon endoscopic assessment, Hubbard and colleagues (2000) discovered that there were no significant differences in regard to parecoxib-associated gastrointestinal adverse events between the parecoxcib and placebo groups (Hubbard et al., 2000). It was also established that parecoxib did not inhibit arachidonate-induced platelet aggregation when comparison was made with ketorolac (Noveck et al., 2004). In this small open-label, single centre, two-treatment period RCT (n = 18), the authors also found that there was non-significant alteration of platelet function from baseline when 40 mg parecoxib was administered twice daily for 6 consecutive days with an attendant 4000U of unfractionated heparin (UFH) given as a bolus on the 5th day which was then followed by a UFH infusion with an initial dose of 10-14U/kg for 36 hours. This proves that

parecoxib does not cause overt bleeding even when it is concomitantly used with UFH. This proves the excellent safety profile of parecoxib compared to other NSAIDs such as ketorolac (Noveck *et al.*, 2004).

2.4 THE ROLE OF PARECOXIB AS AN ADJUNCT TO ROPIVACAINE IN BRACHIAL PLEXUS BLOCK (BPB)

Thus far, there are only two RCTs which investigated the effect of parecoxib as an adjunct to ropivacaine in BPB setting. Liu *et al.* (2013) conducted a randomized controlled trial (RCT) from January 2009 to November 2010 with 150 Chinese patients scheduled for elective forearm surgery, using a multiple-nerve stimulation technique. Patients were allotted randomly into one of these 3 groups: Group A (n = 50) subjects received single-agent 0.25%% ropivacaine for the axillary BPB; Group B (n = 50) received 0.25% ropivacaine and 20 mg of adjunct parecoxib on the axillary BPB; and subjects in Group C (n = 50) received only 20 mg IV parecoxib. The authors documented the sensory and motor blockade duration, and the highest pain score in a 24-hour period following elective forearm surgery.

The results indicated that parecoxib, when used as an adjunct to ropivacaine, prolonged the motor and sensory block times. However, in those who only received the IV parecoxib injection (Group C), such prolongation in sensory and motor block was not observed. Liu and co-workers (2013) also found lower mean pain intensity scores in Group B than the Groups A and C subjects. According to the authors, 20 mg parecoxib given as an adjunct had significantly lengthened the motor (mean motor block duration: 371 minutes (group A) vs 509 minutes (group B); mean difference = 138 minutes; p < 0.001) and sensory (mean sensory block duration: 439 minutes (group A vs 543 minutes (group B); mean difference = 104 minutes; p = 0.001) block times when comparisons were made with group A. However there were no significant differences

with respect to the durations of sensory (mean sensory block duration: 439 minutes (group A) vs 457 minutes (group C); mean difference: 18 minutes; p value = 0.300) and motor (mean motor block duration: 371 minutes (group A) vs 414 minutes (group C); mean difference: 43 minutes; p value = 0.800) blockades between group A and C. Besides, the authors also established that the primary block effectiveness was similar in all three groups (96% for group A, B and C). The authors eventually concluded that adjunct parecoxib significantly lengthened the duration of axillary brachial plexus blockade and lessened postoperative pain in subjects who underwent orthopaedic surgeries to their forearms. However, the authors' findings are still inconclusive due to the small sample sizes employed in their trial and the much lower concentration of ropivacaine (0.25% ropivacaine) that they used in their trial.

There was also another recent study conducted by Cherif and coworkers (2014) in Tunisia. They recruited 118 patients who underwent infraclavicular BPB prior to upper limb surgeries. The patients were randomized into 3 intervention arms; 1) bupivacaine and parecoxib (n=44) (group P), 2) bupivacaine and dexamethasone (n=40) (group D) and 3) bupivacaine and saline (n=34) (group C, placebo controls). The authors established that parecoxib had significantly hastened the time to onset of motor and sensory blockades compared to dexamethasone and saline placebo (mean onset of sensory block: 77.82 seconds (group P) vs 383.45 seconds (group D) vs 302.94 seconds (groupd C), p value <0.05;mean onset of motor block: 120.45 seconds (group P) vs 440.5 seconds (group D) vs 316.24 seconds (group C), p value <0.05). However, dexamethasone was found to enhance the quality of analgesia in comparison with parecoxib and saline placebo (mean Visual Analogue Scale (VAS) score on postoperative day 1: 0.7 (group D) vs 2.68 (group P) vs 2.11 (group C), p <0.05; mean time to first analgesic consumption: 2283 minutes (group D) vs 1248 minutes (group P) vs 1408 minutes (group C). Nevertheless, the generalisability of the findings is still implausible due to the small sample size of this study, the lack of details on the randomization method and procedure employed by the researchers and the lack of controls on confounders that would make the findings accidental (spurious) and inauthentic.

Nonethless, the efficacy of parecoxib (Liu *et al.*, 2013; Cherif *et al.*, 2014) had also been substantiated by other safety data for parecoxib obtained from murine models and a non-randomized double-blind cross-over trial. Kim *et al.* (2011) demonstrated that an epidural injection of COX-2 is a beneficial therapeutic alternative in the clincal management of pain due to its excellent neurotoxicity profile based on their murine model. They also hypothesized that parecoxib might be a suitable alternative to corticosteroid for the management of pain associated with herniated discs and other spinal pathologies due to its antinoceptive effect on the peripheral and central nervous systems. However, since this is just a murine model and did neither incorporate nor investigate the possible synergestic effects of ropivacaine and parecoxib on the nociceptive transmission and modulation in humans, the findings are still not sufficiently conclusive to effect the ubiquitous use of parecoxib in BPB setting.

Apart from that, Martin *et al.* (2007) conducted a non-randomized double-blind cross-over trial involving twelve (n=12) normal individuals to investigate the effect of IV parecoxib at a dose of 1mg/kg on the electrophysiologic recordings of nociceptive flexion reflex (RII). The RII reflex is an objective physiologic index of the spinal transmission of nociceptive signals. Their results indicated that parecoxib, when compared to placebo, significantly reduced the RII stimulus response curve, suggesting a diminishment of the spinal nociceptive signal transmission in. The authors concluded that the constitutive COX-2 isoform regulates the spinal nociceptive transmission processes and the effect of IV parecoxib on the spinal nociceptive transmission blockade is

suggestive of there is no causal relationship between its anti-inflammatory and antinociceptive properties (Martin *et al.*, 2007). Nevertheless, the validity of the study findings had also suffered from the study's sample size, the absence of control subjects and the improper randomization technique used in this trial.

2.5 THE RATIONALE OF THIS STUDY

There is still a paucity of information concerning the role of parecoxib as an adjunct to ropivacaine in supraclavicular BPB, hence creating a gap in clinical knowledge (also known as clinical equipoise) with respect to the exact role of adjunct parecoxib in supraclavicular BPB setting. The only available details that established the utility of adjunct parecoxib in supraclavicular BPB setting are those gained from the small-sized trial conducted by Liu *et al.*, (2013) which are only corroborated by safety data obtained from the murine model (Kim *et al.*, 2011) and the non-randomized cross-over trial (Martin *et al.*, 2007). Furthermore, the usefulness of adjunct parecoxib was only investigated in axillary BPB setting and hence its practicality in other approaches of BPB, for example supraclavicular BPB, is yet to be properly scrutinised. Therefore, this clearly warrants a new clinical trial to further evaluate the extent of adjunct parecoxib's utility in other clinical setting.

2.7 CONCEPTUAL FRAMEWORK

[figure not shown]

Figure 2.1: The conceptual framework of the synergestic effects of parecoxib and ropivacaine on blocking pain signal transmission resulting in an enhanced onset and durations of sensory and motor blockades in BPB.

SECTION 3

RESEARCH OBJECTIVES

3.1 GENERAL OBJECTIVES:

To investigate the effectiveness of parecoxib 20 mg as an adjunct to ropivacaine 0.75% for ultrasound guided supraclavicular block for upper limb surgery.

3.2 SPECIFIC OBJECTIVES:

- To compare the onset of the sensory block between 20mg of parecoxib in 0.75% ropivacaine and plain 0.75% ropivacaine.
- To compare the onset of the motor block between 20mg of parecoxib in 0.75% ropivacaine and plain 0.75% ropivacaine.
- 3. To compare the degrees of sensory and motor block after 30 min between 20mg of parecoxib in 0.75% ropivacaine and plain 0.75% ropivacaine.
- To compare the duration of the sensory block between 20mg of parecoxib in 0.75% ropivacaine and plain 0.75% ropivacaine .
- To compare the duration of the motor block between 20mg of parecoxib in 0.75% ropivacaine and plain 0.75% ropivacaine .

3.3 RESEARCH QUESTIONS

- Do subjects receiving 20mg of parecoxib in 0.75% ropivacaine significantly differ in terms of the onset of the sensory block when compared to those recipients of single-agent 0.75% ropivacaine?
- 2. Do recipients of 20mg of parecoxib in 0.75% ropivacaine significantly differ with respect to the onset of the motor block when they are compared with those recipients of single-agent 0.75% ropivacaine?

- 3. Is there any significant difference between subjects receiving 20mg of parecoxib in 0.75% ropivacaine and single agent 0.75% ropivacaine with regard to the degrees of sensory and motor block?
- 4. Are those receiving 20mg of parecoxib in 0.75% ropivacaine significantly differ from the recipients of single-agent 0.75% ropivacaine with respect to the duration of sensory block?
- 5. Is there any significance difference in terms of duration of motor block between the recipients of 20 mg parecoxib in 20% ropivacaine and those receiving single-agent 20% ropivacaine?

3.4 RESEARCH HYPOTHESES

- Null hypothesis (H₀): There is no significant difference in the onset of the sensory block is faster in 20mg of parecoxib in 0.75% ropivacaine in comparison to plain 0.75% ropivacaine.
- Null hypothesis (H₀): There is no significant difference in the onset of the motor block is faster in 20mg of parecoxib in 0.75% ropivacaine in comparison to plain 0.75% ropivacaine.
- Null hypothesis (H₀): There are no significant differences in the degrees of sensory and motor block after 30 min is higher in 20mg of parecoxib in 0.75% ropivacaine in comparison to plain 0.75% ropivacaine
- Null hypothesis (H₀): There is no significant difference in the duration of the sensory block in 20mg of parecoxib in 0.75% ropivacaine in comparison to plain 0.75% ropivacaine
- Null hypothesis (H₀): There is no significant difference in the duration of the motor block in 20mg of parecoxib in 0.75% ropivacaine in comparison to plain 0.75% ropivacaine.

SECTION 4

RESEARCH METHODOLOGY

4.1 STUDY DESIGN

A prospective, single center, two-parallel group, single (observer)-blinded controlled trial involving surgical patients undergoing upper limb surgeries at the HUSM surgical theatres.

4.2 STUDY PERIOD AND PERIOD OF RECRUITMENT

The total study duration is 10 weeks and the period of patient recruitment is from 20th June 2017 till 28th August 2017.

4.3 TRIAL CENTRE

Hospital Universiti Sains Malaysia (HUSM) is the main teaching hospital for the Eastern Coastal states of Peninisular Malaysia. It is situated in Kubang Kerian, Kelantan and handles primary-care referrals from all the states in the eastern region of Peninsular Malaysia (Kelantan, Terengganu and Pahang). Hence, it can be considered as one of the chief tertiary care centres that dispenses a modern specialty care for nearly a third of the whole population in Peninsular Malaysia.

Annually, HUSM accepts almost 2000 surgical cases, of which nearly 19.65 percent are elective or semi-emergency surgical patients that require upper limb procedures (393 cases). This provides the study investigators ample resources for the acquisition of patients that meet the trial criteria which ensures in the accomplishment of the intended sample size.

4.4 REFERENCE AND SOURCE POPULATION

The reference population is all elective or semi-emergency surgical patients who underwent upper-limb surgical procedures and supraclavicular BPB in Kelantan. The source population is all elective or semi-emergency surgical patients receiving upperlimb surgical procedures and supraclavicular brachial plexus block who resided in Kota Bharu.

4.5 SAMPLING FRAME

All subjects who fulfilled the eligibility criteria (both inclusion and exclusion) and had upper-limb surgical procedures and supraclavicular BPB in the HUSM between 20th June 2017 and 28th August 2017 were included in the sampling frame.

4.6 SAMPLING METHOD

Despite sufficient potential subjects for their recruitment into this trial, convenient sampling had to be used due to the time constraint imposed by the urgency for thesis submission within the tight submission window (early November).

4.7 STUDY SUBJECTS

All patients that fulfilled the eligibility (inclusion and exclusion) criteria and consented for study participation.

4.8 ELIGIBILITY CRITERIA

4.8.1 Inclusion criteria

- I) Aged between 18 to 70 years old
- II) Subjects with the American Society of Anaesthesiologists (ASA) physical status grade

1 to 2

III) The expected duration of surgery was between 1 and 4 hours.

4.8.2 Exclusion criteria

- I) Subjects who refused to brachical plexus block (BPB)
- II) Known allergies to parecoxib, other NSAIDS and anaesthetic agents.
- III) Pregnancy
- IV) History of prior brachial plexus injury
- V) History of chronic pain that requires long-term use of analgesic medications

VI) Coagulopathy

VII) Systemic infection or local infection at the site of injection

VII) Known neuropathy for the limb undergoing surgical procedures.

4.9 OPERATIONAL DEFINITIONS OF VARIABLES

a) Independent variables

i) **Age:** The age of patients (in years) when BPB was performed. Measured and recorded as a strictly positive continuous variable.

ii) **Gender:** The gender of a subject. Recorded as a categorical variable with 0 = male (the baseline group) and 1 = female.

iii) **Ethnicity:** Subject's racial origin. Recorded as a categorical variable with 0 = Malay (the baseline group), 1 = Chinese, 2 = Indian, 3 = Others (such as Siamese)

iv) The American Society of Anaesthesiologist (ASA) grades: Recorded as a categorical variable with 0 =Grade 1 (the baseline group), 1 =Grade 2.

v) **Weight:** The weight of a study participant measured in kilograms measured during he pre-surgical assessment. Recorded as a strictly positive continuous variable.

vi) **Intervention groups:** Recorded as a categorical variable with 0 = 0.75% Ropivacaine only group (the baseline group) and 1 = 0.75% Ropivacaine + adjunct 20 mg parecoxib group.

b) Dependent (outcome) variables

i) **Onset of sensory block:** Time required for a decrease of sensation to 30% or less by comparison to the contralateral limbs as a reference (Duma *et al.*, 2005). Measured in minutes and recorded as a numerical variable.

ii) **Onset of motor block**: the time from injection of local anesthetic mixture until a reduction in motor power to grade 3 or 4 ensued (Ammar and Mahmoud, 2012). Measured in minutes and recorded as a numerical variable.

iii) **Sensory block duration:** The time from injection of local anaesthetic mixture to complete recovery from cold and pain sensation as tested by an alcohol swab and pin prick respective in all dermatomes of the brachial plexus (C5-T1). Measured in hours_and recorded as a continuous variable

iv) **Motor block duration:** the time from injection to complete recovery of motor function in all nerve dermatomes. Measured in hours and recorded as a continuous variable.

v) **Sensory and motor blockades at 30 minutes:** The presence of complete sensory (grade 2) and motor (grade 4) blockades at 30 minutes following the BPB institution.

c) Other relevant clinical variables

i) **Time 1st PCA:** The time taken from the end of the surgery until the delivery of the first PCA morphine. Measured and recorded as a strictly positive numerical variable

ii) **Volume PCA:** The total volume of PCA morphine administered to the patients after surgery until the patient was discharged from the ward. Measured in mls and recorded as a numerical variable.

iii) PCA demand: The total frequency of morphine demand over a period of 24 hours.Measured and recorded as a strictly positive numerical count variable.

iv) **Sensory block grades:** This was assessed using the a 3-point scale utilised by Crews *et al.* (2002). There are 3 grades for this variable;

- Grade 0 = normal sensory response
- Grade 1 = reduced sensory perception (partial sensory blockade)
- Grade 2 = no sensation (complete sensory blockade).

Recorded as 0 = normal (baseline group), 1 = reduced, 2 = absent.

v) **Motor block grades:** The scale used by Borgeat, Ekatodramis and Durmont (2001) are employed to grade the magnitude of motor block. This scale has 4 grades:

- Grade 1: ability to flex or extend the forearm
- Grade 2: ability to flex or extend only the wrist and fingers
- Grade 3: ability to flex or extend only the fingers
- Grade 4: inability to move the forearm, wrist, and fingers

Recorded as 0 = Grade 1 (baseline group), 1 = Grade 2, 2 = Grade 3, 3 = Grade 4.

vi) **Surgical sites:** The exact location where surgery to the upper limb was carried out. Recorded as 1 = Arm, 2 = Forearm, 3 = Hand, 4 = Fingers.

vii) **VRS :** The visual rating score (VRS) which was recorded at 1, 2, 4, 12, 24 hours post operatively. Its range is between 0 and 10. Recorded as a strictly-positive numerical variable.

viii) **Preoperative VRS:** The VRS recorded prior to supraclavicular BPB.

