THE EFFICACY OF PARECOXIB 20MG AS AN ADJUNCT IN 0.75% ROPIVACAINE IN SUPRACLAVICULAR BRACHIAL PLEUXS BLOCK FOR UPPER LIMB SURGERY

Primary Investigator:	1) DR [name] (MBBS (Manipal), MMed Anaesthesiology (USM))
Co-investigators:	1) DR [name] (MBChB BAO (Queen's University of Belfast), PhD (Newcastle University))
	2) DR [name] (MD (UKM), MMed Anaesthesiology (USM))
	3) DR [name] (MD (USM), MMed Anaesthesiology (USM))
	4) DR [name] (MD (UIA), MSc Medical Statistics (USM))

UNIVERSITI SAINS MALAYSIA

Date of report: 30th NOVEMBER 2017

(Minor amendment: 20th MARCH 2018)

NCT ID: To be assigned

THE EFFICACY OF PARECOXIB 20MG AS AN ADJUNCT IN 0.75% ROPIVACAINE IN SUPRACLAVICULAR BRACHIAL PLEUXS BLOCK FOR UPPER LIMB SURGERY

ABSTRACT

Introduction

Brachial plexus block (BPB) is a critical method in providing anaesthesia for upper limb surgery. Parecoxib, a specific COX-2 inhibitor, has the potential as an adjunct for 0.75% ropivacaine in supraclavicular BP block setting.

Objectives

To investigate whether the efficacy of supraclavicular brachical block is enhanced by the addition of 20 mg parecoxib to 0.75% ropivacaine in patients undergoing upper limb surgery.

Methods

This is a double-blind, active-controlled, parallel group, prospective randomized clinical trial conducted between 20th June and 28th August 2017 involving eighty six (n=86) adults whose age were between 18 and 65 years old, with ASA grade I or II and undergoing various upper limb surgeries whose durations were between 1 and 4 hours. The subjects were block-randomized in 1:1 ratio into two groups; group 1 received adjunct IV parecoxib and 0.75% ropivacaine whilst group 2 received 0.75% ropivacaine alone. The primary end-points are the duration and onset of sensory and motor block and the proportions of complete motor and sensory block at 30 minutes following supraclavicular BP block. The significance of the differences in trial endpoints were statistically tested using Mann-Whitney and Chi-square tests.

Results

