Eighty six (n=86) subjects were randomised to either group and analysed. There were higher durations of sensory and motor blocks in the adjunct parecoxib + ropivacaine group compared to the ropivacaine-only groups (sensory block duration: 6.5 hours vs 5.0 hours, median difference = 1.5 hours, p value <0.001; motor block duration: 4.84 hours vs 3.86 hours, median difference = 0.97 hours, p value <0.001). No significant differences between the two intervention arms with respect to sensory (9 minutes vs 9 minutes, median difference = 0 minute, p value = 0.511) and motor blockades (17 minutes vs 18 minutes, median difference = 1 minute, p value = 0.832) onset. Besides, there no significant difference in terms of complete sensory and motor blockades at 30 minutes post supraclavicular block between parecoxib + ropivacaine and ropivacaine-only groups (sensory blockade at 30 minutes: 100% vs 97.7 %, p value = 1.000; motor blockade at 30 minute = 100% vs 97.7%, p value = 1.000). No adverse events were reported in both intervention arms and the trial was not ended prematurely.

Conclusion

Adjunct parecoxib significantly enhances the durations of sensory and motor blockades, but not their onset and complete sensory and motor block at 30 minutes following supraclavicular brachial plexus block.

(395 words)

SECTION ONE

INTRODUCTION

Brachial plexus block (BPB) has enjoyed ubiquitious popularity for upper limb surgeries (Raju and Coventry, 2013). It provides sufficient anaesthesia for surgical procedures involving upper limbs due to the propinquity of the brachial plexus' trunks and division when they pass the first rib (Gamo *et al.*, 2014).

There are a few common techniques for BPB and one of the most frequentlyutilised one is supraclavicular BPB (Raju and Coventry, 2013). It is not only an efficient mode of anaesthesia intraoperatively, but it is can also provide a quick-onset and dense anaesthesia for surgical procedures that involve the proximal mid-humerus down to the distal hand with excellent safety profile (Raju and Coventry, 2013; Gamo *et al.*, 2014). The supraclavicular block (SCB) is performed above the clavicle and aims at the level of the nerve trunks or division of brachial plexus (BP). Other frequently-employed alternatives include infraclavicular block, interscalene block and axillary BPB (Raju and Coventry, 2013).

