In another study by Kapral and others (1994), the researchers adapted the method developed by Ting and Sivagnanratnam and used it for the supraclavicular paravascular approach of BPB. The authors investigated the utility and impact of ultrasonic cannula guidance for supraclavicular puncture of the brachial plexus sheath against the axillary approach in terms of success, rate, onset and the frequency of complications. They found that 95% of the subjects in both groups experienced satisfactory analgesia. Nevertheless, 25% of subjects in the axillary approach group experienced incomplete sensory block whilst none of the subjects in the supraclavicular paravascular approach had incomplete sensory block. The authors concluded that the ultrasonography-guided approach for the supraclavicular block is comparatively as safe as the axillary approach, with a larger extent of block than the axillary approach.

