Besides, Chan and colleagues (2003) also researched the utility of ultrasoundguided supraclavicular approach for BPB. The rationale for further researching and developing this technique, according to the authors, is that it can be utilised to precisely and accurately locate the brachial plexus, hence reducing the procedure-related pain associated with imprecise anatomical landmark localisation based on the trial and error approach and potential pneumothorax. The authors observed that in 40 patients who received BPB for their elective upper-limb surgeries via this new approach, low pain score during their postoperative care at post-anaesthesia care unit (PACU) (mean score of 0.3 out of 10) and high satisfaction in regard to pain control (median score of 9 out of 10) were reported. Two failures were recorded which were attributed to subcutaneous injection of bupivacaine and partial intravascular local anaesthetic injection which led to block failure at 30 minutes post injection. Two study participants experienced complications postoperatively which include Horner's syndrome and transient paraesthesia that lasted for less than 48 hours. No incidence of pneumothorax was reported. The findings of this study were further corroborated by a subsequent study by Chan *et al.* (2007) who demonstrated that the ultrasound guidance enhanced the success rate of axillary BPB (defined as the absence of sensation in upper limb areas supplied by the median, ulnar and radial nerves at 30 minutes following axillary BPB) in 188 patients who had elective hand surgeries. Apart from that, there were less number of patients in comparison to the other group whose subjects underwent axillary BPB guided only by a nerve stimulator. The findings of this trial, hence, conclusively showed the superiority of this ultrasound-guidance technique over the other alternative methods for BPB.

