 - After skin preparation and draping, the probe was next placed in the supraclavicular fossa and subcutaneous infiltration will be given on the targeted needle side

- The needle was then inserted from lateral to medial direction in the long axis of the transducer (in-plane technique).
- Nineteen (19) ml of 0.75% ropivacaine and 1 ml of 20 mg of parecoxib
 (Group I: parecoxib + ropivacaine) or 19 mls of 0.75% alone plus 1 ml of
 normal saline (Group II: ropivacaine alone) was then injected at the
 "corner pocket". Adrenaline was not added into any solution.
- The remaining 5 ml was later injected to a point approximately level with the superior/ cephalad aspect of the subclavian artery, but no further than 1 cm lateral to the artery

Block performance-related pain was then evaluated immediately after removing the needle by asking the patient to verbally quantify the level of pain using a score between 0 to 10 (0 meaning no pain, 10 meaning excruciating pain). The study participants were withdrawn from the trial and rescue medications were given if one of the following withdrawal criteria occurred:

- Patient developed local anaesthetic toxicity (seizure)
- Patient developed hemodynamically instability bradycardia/hypotension)
- Patient developed anaphylaxis

The procedures for the assessment of sensory and motor block are as follows:

- Assessment of sensory block:
 - Sensory blockade was assessed every 5 minutes up to 30 minutes following the completion of administration of intervention.
 - Sensory loss was confirmed by the loss to cold sensation using 10 mls cold saline bottle and pinprick sensation using 23G needle in all dermatomes supplied by the brachial plexus (C5-T1).
 - Time zero was defined as the time at which LA was completely injected.

- Sensory block success was defined as complete pin-prick sensory blockade (grade II based on the grading scale employed by Crews *et al.* (2002)) in all dermatomes of the brachial plexus (C5-T1).
- The block was considered incomplete if any supplemental local anesthetic is needed for complete anesthesia.
- The block was considered failed if the desired volume did not provide complete anesthesia or conversion to general anaesthesia was required prior to surgery.
- General anaesthesia was routinely performed with intravenous induction (sedation) agent, short acting opiods and muscle relaxant
- Assessment of motor block:

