5.3.2 The degrees of sensory and motor block

Based on inspection of table 5.5, there are no significant differences with regard to the degrees of sensory and motor block at 30 minutes following supraclavicular BPB between the two intervention arms (p values of 1 for both outcome parameters). The odds ratio cannot even be computed because there are cells with 0 count.

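### Complete block at 30 minutes is a listed primary end-point that sits near its ceiling and was never powered, so the abstract's negative conclusion on it is not supported

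*Combined protocol and SAP*

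**What the plan says.** The abstract's Methods state: "The primary end-points are the duration and onset of sensory and motor block and the proportions of complete motor and sensory block at 30 minutes". Section 4.9 gives the definition: "The presence of complete sensory (grade 2) and motor (grade 4) blockades at 30 minutes following the BPB institution". The degree of block at 30 minutes is also the third specific objective (Section 3.2) and has its own null hypothesis (Section 3.4).

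Section 4.13 tests it with Pearson chi-square or Fisher's exact test at 0.05. The footnote to Table 4.1 selects Fisher when more than 20% of cells have an expected count below 5. Section 4.11 sizes the trial on motor and sensory block duration and does not mention this outcome.

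The background gives some idea of the rate to expect. For the axillary-block trial used for sizing, Section 2.4 reports that "the primary block effectiveness was similar in all three groups (96% for group A, B and C". Section 2.1 cites an ultrasound-guided comparison of supraclavicular and axillary block ("They found that 95% of the subjects in both groups experienced satisfactory analgesia"). It also cites a 40-patient supraclavicular series with two failures, which "led to block failure at 30 minutes post injection".

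The result for sensory and for motor block alike was 43/43 against 42/43, p = 1.000 (Table 5.5). Section 5.3.2 gives no effect estimate: "The odds ratio cannot even be computed because there are cells with 0 count". The abstract concludes that parecoxib enhances duration, "but not their onset and complete sensory and motor block at 30 minutes following supraclavicular brachial plexus block". Section 6.4 says the sample presumably gives at least 90% power and does not say for which outcome.

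**The concern.** When nearly every control patient is expected to have a complete block, there is almost no room for the adjunct to show a benefit. A non-significant test is then close to certain whether or not parecoxib helps. Reading p = 1.000 as no enhancement turns an unanswerable question into a negative answer. The 90% power statement invites the same reading, because nothing ties it to duration. At stake are one of the five specific objectives and one clause of the abstract's conclusion.

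**Working it through.** **Inputs.** 43 per arm and 1:1 allocation (abstract, Section 4.10.1, Table 5.5). Alpha 0.05 (Section 4.13); sidedness is not stated, so two-sided is assumed. Control success of 95–96% is an assumption taken from Sections 2.1 and 2.4, since the plan states no rate (two failures in 40 is 38/40 = 95%). Parecoxib success is set at 100%, the largest gain possible.

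**1. The plan's own figures.** n per arm = 2(1.960 + 1.282)² × SD² / difference².
- Sensory duration: 21.01 × 140²/104² = 38.1, so 39.
- Motor duration: 21.01 × 139²/138² = 21.3, so 22.

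Both match Section 4.11, although only before any allowance for the 20% attrition it mentions; that is a separate matter. At 43 per arm the same formula gives about 93% power for sensory and over 99% for motor duration. The 90% statement is therefore fair for duration under the plan's assumptions.

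**2. Which test applies.** With f failures in total and equal arms, each failure cell has expected count f/2. If f is below 10, two of the four cells (50%) fall below 5, and the plan's rule selects Fisher. The reported p = 1.000 without a chi-square statistic agrees with that, and Fisher on 43/43 against 42/43 reproduces p = 1.000.

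**3. Failures needed.** With no parecoxib failures and k control failures, the two-sided Fisher p is 2 × C(43,k)/C(86,k).
- k = 5: p = 0.055.
- k = 6: p = 0.026.

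At least 6 against 0 are needed. At 96% control success the expected number is 43 × 0.04 = 1.7.

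**4. Power.** Against a perfect parecoxib arm, power = P(X ≥ 6) with X binomial(43, 1 − control success).

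| Control success | Power |
|---|---|
| 97.7% (observed) | 0.04% |
| 96% | 0.70% |
| 95% | 1.9% |
| 92% | 12.6% |
| 90% | 25.7% |
| 85% | 64% |
| about 82% | 80% |

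For 96% against 100%, about 197 per arm would be needed for 80% power with Fisher's test.

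**5. What the data show.** Difference = 1 − 42/43 = 0.0233. The Wilson 95% limits are 0.918 to 1 for 43/43 and 0.879 to 0.996 for 42/43. Newcombe's interval is then:
- lower: 0.0233 − √[(1 − 0.918)² + (0.996 − 0.977)²] = −0.061
- upper: 0.0233 + √[(1 − 1)² + (0.977 − 0.879)²] = +0.121

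The interval runs from about 6 points worse to 12 points better, and is the same for sensory and for motor block.

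**The case against.** The strongest objection is that the 95–96% is borrowed. The 96% is a block-effectiveness rate from an axillary technique with 0.25% ropivacaine, not grade 2 sensory and grade 4 motor block after supraclavicular 0.75% ropivacaine. Section 2.1 also cites 88% complete block with a single injection, though in radial territory at 20 minutes. This stands as a limit on size. A reader might infer that the end-point simply has under 1% power, but the documents do not support that as a flat statement: it holds only at about 96% control success or higher and under Fisher's test. Uncorrected Pearson would give 9.2% at 96%, but the plan's rule does not select it there. Power stays low across the cited 95–96% range in any case.

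A reader might also infer that the outcome carries no information. That goes too far. The interval makes a fall of much more than 6 points unlikely, and block success at 30 minutes is an outcome used in the cited literature, so reporting it is not a fault.

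The primary label appears only in the abstract, and the Introduction singles out duration. Section 6.4 concedes that a small sample may fail to reject the null hypothesis and that a large p value does not mean a small effect. The Results wording reports only non-significance, and Section 7 mentions onset but not complete block. All of this narrows the fault to the abstract's conclusion and the unrestricted power statement, but removes neither.

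**Conclusion.** The concern holds in this form: a listed primary end-point was left out of the sizing and had roughly 1–2% power at the cited 95–96% success rates, even against a perfect parecoxib arm. It would have had 26% at 90%, and control success would have to be about 82% or lower for 80%. These figures assume 43 per arm, a two-sided 0.05 level and the plan's rule selecting Fisher.

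The abstract's claim of no enhancement, and the 90% power statement as applied to this outcome, are not supported. Nor do the data show that parecoxib improves complete block. The duration results are untouched. A reader might think that extra grade boxes on the case report form would cure the problem, but recruitment and analysis are finished, so new boxes cannot recover grades that were not recorded.

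**What to change.** Four changes need only existing counts and revised text:

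- Treat the 30-minute proportion as descriptive.
- In Section 5.3.2 and Table 5.5, replace the uncomputed odds ratio with the risk difference and 95% CI: +2.3 points, about −6 to +12, for sensory and for motor block.
- Reword the abstract's conclusion on this outcome to: *block was near-complete in both arms at 30 minutes, so a difference could not be assessed*.
- In Section 6.4, limit the 90% power statement to the two duration outcomes.

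One addition is conditional. Section 4.10.2 says "Sensory blockade was assessed every 5 minutes up to 30 minutes", and motor block followed the same schedule. If those grades were retained, time to complete block could be added as a supplementary interval-censored comparison, censored at 30 minutes. It would differ from the onset outcomes, which use partial thresholds. The part of the case report form available for review has boxes only for the 30-minute grade, and its later pages were not available, so retention cannot be judged. The sensory coding must be reconciled first: Section 4.9 codes complete block as 2 and normal as 0, while the form codes complete as 0 and normal as 2. Without that, an analysis of time to grade 2 could time normal sensation. If the grades were not kept, this analysis belongs to a future trial.
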